2.5.2 End of Part 1 (July 2022)

When the high renin cohort (PRA > 1 ng/mL/h) was introduced in Protocol v6.0 (Protocol Amendment 5), it increased enrolment and extended the timelines for final database lock. In order to maintain the End of Phase 2 (EOP2) timelines, it was decided to add an interim analysis when all subjects complete Part 1, focusing on the outputs necessary to support EOP2.

A separate team will receive the Part 1 results and prepare for EOP2; the main study team will remain blinded until the end of Part 2.

3 STUDY ENDPOINTS

3.1 Efficacy Endpoints

3.1.1 Primary Endpoint

The primary endpoint is the change in office-measured (mean of last 2 of 5 unattended measurements using an automated oscillometric sphygmomanometer device after approximately 5 minutes of rest in the seated position) systolic blood pressure (SBP) from baseline to the end of Study Week 8.

3.1.2 Secondary Endpoints

The protocol describes as secondary endpoints the following:

- Change in 24-hour ambulatory blood pressure monitoring (ABPM) parameters (systolic and diastolic) from baseline to the end of treatment.
- Change in office-measured SBP from baseline to the end of Study Weeks 1, 2, 3, 4, 5, 6, and 7.
- Change in office-measured diastolic blood pressure (DBP) from baseline to the end of Study Weeks 1, 2, 3, 4, 5, 6, 7, and 8.
- Proportion of subjects who achieve office-measured BP of $\leq 130/80$ mm Hg by the end of Study Week 8.

3.2 Pharmacodynamics Endpoints

The protocol describes as pharmacodynamics endpoints the following:

- Change in plasma 11-deoxycortisol and PRA from baseline to the end of Study Week 4 and to end of follow up (i.e. end of Study Week 12 for Part 1 and end of Study 10 for Part 2).
- Change in serum aldosterone, cortisol, and 11-deoxycorticosterone concentration from baseline to the end of Study Week 4 and to end of follow-up.

3.3 Pharmacokinetic Endpoints

The protocol describes as pharmacokinetics endpoints the following:

- PK parameters, including, if feasible, of area under the plasma concentration versus time curve (AUC), maximum plasma concentration (Cmax), time to maximum concentration (Tmax), and half-life (t_{1/2}) will be summarized descriptively for Randomization (baseline) and Study Weeks 1, 4, and 8

3.4 Safety Endpoints

The protocol describes as safety endpoints the following:

- Incidence and severity of all spontaneously reported adverse events (AEs)
- Changes in vital signs (standing SBP, standing DBP, body temperature, heart rate, and respiratory rate)
- Changes in electrocardiogram parameters (including cardiac intervals: PR, QRS, QT, and corrected QT interval using Fridericia's formula)
- Changes in clinical laboratory assessments (hematology, chemistry, coagulation, and urinalysis)
- Change in office-measured SBP from Study Week 8 (end-of-treatment period to end of follow up (i.e. end of Study Week 12 for Part 1 and end of Study 10 for Part 2).

4 ANALYSIS SETS

4.1 Analysis Set Definitions

The following analysis sets are defined in this study:

4.1.1 All Randomized Set

The All-Randomized Set includes all randomized subjects. This analysis set will be used for summaries of subject study disposition, with subjects analyzed according to the randomized study treatment group.

4.1.2 Full Analysis Set (FAS)

The FAS includes all randomized subjects who have received at least 1 dose of randomized study treatment (MLS-101 or placebo). The FAS will be the primary set for efficacy analyses. In analyses performed on the FAS, unless otherwise specified, subjects will be analyzed according to the randomized study treatment group.

4.1.3 Per Protocol Set (PPS)

The Per Protocol Set includes all subjects in the FAS who have completed the Study Week 8 visit without any major protocol violations that could influence the validity of the data for the primary efficacy evaluations. In the analyses based on PPS, subjects will be analyzed according to the randomized study treatment group. All criteria to exclude subjects from the PPS will be made based on a blinded review of the data prior to the unblinding of the study.

A subject may be excluded from the Per Protocol Analysis Set if any of the following criteria are met:

- Not meeting Inclusion/Exclusion criteria
- Use of prohibited medications. Subjects using rescue medications will not be excluded from the PPS unless subjects have met other criteria excluding them from the PPS
- Not compliant with the study drug
- Out of window efficacy assessment at study Week 8 visit

Alternate criteria for exclusion from the Per Protocol Analysis Set may be applied to accommodate unforeseen events that occurred during the conduct of the study.

Analyses on Per Protocol Analysis Set will be of supportive purpose and limited to primary endpoint (i.e., "product Estimand").

4.1.4 Safety Analysis Set (SAF)

The Safety Analysis Set includes all enrolled subjects who received at least one dose of study treatment (MLS-101 or placebo). In analyses performed on the Safety Analysis Set, subjects will be analyzed according to their actual treatment received.

4.1.5 PK/PD Analysis Set (PKPD)

PK/PD Analysis Set includes all subjects in the SAF who have sufficient data available for the analysis of pharmacokinetic and pharmacodynamic measurements. In the analyses based on PKPD, subjects will be analyzed according to the actual treatment received.

4.2 Protocol Deviations

All protocol deviations are recorded in the Clinical Trial Management System, InfoLink2, and will be included in a data listing of deviations.

5 DATA HANDLING

5.1 Computing Environment

All descriptive statistical analyses will be performed using SAS statistical software (Version 9.4), unless otherwise noted. Medical History and adverse events will be coded using MedDRA version 24.0. Concomitant medications will be coded using World Health Organization (WHO) Drug version September 2021.

5.2 Data Conventions

For any events on or after the first IMP administration, study day is calculated as:

event date – date of first administration of IMP + 1.

As such, the first dose date is study day 1. For any events before the first administration date, study day is calculated as:

event date – date of first administration of IMP.

5.3 Methods of Pooling Data

Unless otherwise noted, summaries will be provided on the data from Part 1 and Part 2 separately, with no pooling of dose groups for tabulations. Analyses will be performed within each part separately.

5.4 Withdrawals, Dropouts, Loss to Follow-up

Subjects who withdraw from treatment will still be followed until End of Study, unless they withdraw from study also. Withdrawals will not be replaced.

5.5 Visit Windows

No analysis visit windowing will be performed for this study with the exception of early termination visits (specifically the End of Treatment visit, which is recorded on the eCRF as Week 8/EOT). Early termination assessments will be re-numbered to an analysis visit based on their windowed visits defined by actual study day (see table below).

For the supplemental Estimand (defined in Section 6.4.1.5) only, post-treatment visits will also be re-numbered based on their windowed visits defined by actual study day. Specially, this refers to the End of Study visit at Week 12 (Part 1) or Week 10 (Part 2). This is because the supplemental

Estimand uses all observed data, regardless of whether they are on treatment or not. As the supplemental Estimand is only defined for SBP, this is the only variable for which the EOS visit windowing needs to be applied.

The following analysis visit windows will apply to early termination visits:

| Visit | Target Study Day | Analysis Window |
|--------------------|--------------------|--|
| Baseline | Day 1 | ≤ Day of first dose in Double-blind treatment period |
| Week 1 – Visit 7 | Day 7 (± 2) | Day 2 – Day 10 |
| Week 2 – Visit 8 | Day 14 (± 2) | Day 11 – Day 17 |
| Week 3 – Visit 9 | Day 21 (± 2) | Day 18 – Day 24 |
| Week 4 – Visit 10 | Day 28 (± 2) | Day 25 – Day 31 |
| Week 5 – Visit 11 | Day 35 (± 2) | Day 32 – Day 38 |
| Week 6 – Visit 12 | Day 42 (± 2) | Day 39 – Day 45 |
| Week 7 – Visit 13 | Day 49 (± 2) | Day 46 – Day 52 |
| Week 8 – Visit 14 | Day 56 (± 2) | ≥ Day 53 |
| Week 9 – Visit 15 | 3 days post EOS | N/A |
| Week 12 – Visit 16 | Day 84 (± 2) | N/A |

If more than one assessment occurs within a single visit window, the analysis will take the nominal visit assessment if there is a nominal visit or the later assessment if there is no nominal visit assessment.

For by-visit summaries, endpoints will be analyzed according to the nominal visits (i.e. assigned visit). Unscheduled measurements will not be included in by-visit summaries but will contribute to the Baseline timepoint and/or minimum/maximum/worst value (e.g. shift table), if applicable.

Listings will include all visit data, including unscheduled visits, in chronological order based on visit date.

[figure not shown]

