#### **8.2.4. Electrocardiogram**

Single 12-lead ECGs will be recorded at Screening/start of Placebo Run-in, Randomization (Baseline), and at the Study Week 8 (end-of-treatment) visit. Parameters to be recorded include PR, QRS, and QT intervals, and corrected QT interval using Fridericia's formula.

Measurements will be taken after the subject has rested for at least 10 minutes in a supine position using a 12-lead (I, II, III, aVR, aVL, aVF, V1-V6) ECG system over a duration of 10 seconds. The chart speed will be set at 25 mm/sec. ECG changes consistent with hyperkalemia will require confirmation of potassium levels at a local laboratory.

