6.7.3 Vital Signs and Physical Examinations

Height from the screening visit, weight, BMI, and vital sign results (temperature, pulse, and respiratory rate) and change from baseline values will be presented in data listings by subject.

Height, weight, BMI and vital sign summaries of observed values and changes from baseline will be presented by treatment group and each applicable visit/at scheduled timepoint.

In addition, the number and percentage of subjects who experienced a ≥ 20 bpm increase from baseline in pulse, will be summarized. In these summaries, the first occurrence of the event per subject will be summarized. Investigator assessment of body system (Normal, Abnormal) performed during the complete physical examination will be listed but not summarized.

6.7.4 12-Lead Electrocardiogram (ECG)

ECG parameters (PR, RR, QRS, QT, QTcB, and QTcF intervals) will be summarized descriptively in summary tables using observed values and change from baseline by treatment groups and scheduled visits. In addition, shift from baseline of investigator's overall ECG evaluation (i.e., normal, abnormal not clinically significant, abnormal clinically significant) at the Study Week 8 visit will be summarized using counts and percentages of subjects.

ECG results (PR, RR, QRS, QT, QTcB, QTcF, and overall ECG evaluation [Normal, Abnormal not Clinically Significant, Abnormal Clinically Significant]) will be presented in data listings by subject and visits.

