6.7.5 Standing BP

Standing BP will be measured at Screening, Randomization, Study Week 1, Study Week 8 with the AOBP device. In addition, standing BP will be measured if a subject reports symptom of hypotension and will be assessed weekly until symptoms resolve.

Standing BP will be summarized descriptively in summary tables using observed values and change from baseline by treatment groups and scheduled visits. In addition, the number and percentage of subjects who experienced a decrease in SBP \geq 20 mm Hg or DBP \geq 10 mm Hg from sitting to standing position within 3 minutes of standing will be summarized.

A listing of all standing BP data will be provided.

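### SAP 5.5 re-numbers every early Week 8/EOT visit by study day; read literally, this drops an end-of-treatment ECG taken before Day 53 from all the ECG summaries in SAP 6.7.4

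*SAP*

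**What the plan says.** SAP 5.5 applies no visit windowing except to early termination visits: "specifically the End of Treatment visit, which is recorded on the eCRF as Week 8/EOT". For those, "Early termination assessments will be re-numbered to an analysis visit based on their windowed visits defined by actual study day". The window table assigns Days 2 to 10 to Week 1, then seven-day blocks up to Days 46 to 52 for Week 7, and Day 53 onward to Week 8. A second rule re-numbers the End of Study visit for the supplemental estimand. Only that rule is limited to SBP: "this is the only variable for which the EOS visit windowing needs to be applied".

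If two assessments fall in one window, "the analysis will take the nominal visit assessment if there is a nominal visit". The section then adds: "For by-visit summaries, endpoints will be analyzed according to the nominal visits (i.e. assigned visit").

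For ECG, Protocol 8.2.4 says: "Single 12-lead ECGs will be recorded at Screening/start of Placebo Run-in, Randomization (Baseline), and at the Study Week 8 (end-of-treatment) visit". SAP 6.7.4 summarizes ECG parameters by treatment group and scheduled visit. The shift in the investigator's overall ECG evaluation "at the Study Week 8 visit will be summarized using counts and percentages of subjects".

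For standing BP, SAP 6.7.5 says: "Standing BP will be measured at Screening, Randomization, Study Week 1, Study Week 8 with the AOBP device". Extra measurements are taken if a subject reports symptoms of hypotension. Part 1 spot urine is collected on Day 1 and at Week 8 (Protocol Table 1, footnote q).

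**The concern.** Re-numbering by study day suits a measure taken every week: an EOT office BP on Day 20 is a sensible Week 3 value. It does not suit an assessment that exists after baseline only because the subject reached the end-of-treatment visit. Moving that record by study day puts it in a week where the table has no place for it.

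The subjects affected are those who leave before Week 8. Their EOT ECG is normally their only post-baseline ECG, and this trial treats ECG changes consistent with hyperkalemia as a finding that needs a potassium check (Protocol 8.2.4). If that record goes to the listings alone, the by-arm ECG tables describe mainly the subjects who stayed to Week 8.

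**Working it through.** The plan gives no figure to reproduce here, so the check sets the window table in SAP 5.5 against the visit schedule.

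**1. Scope of the rule.** The EOT re-numbering names no variable. The restriction to SBP belongs to the End of Study rule. On its face, the EOT rule therefore covers safety data.

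**2. Mapping EOT days to weeks.** I took every possible EOT day from Day 2 to Day 58, the end of the ±2-day window around Day 56. That is 58 − 2 + 1 = 57 days. Each was assigned its SAP 5.5 week and compared with the weeks in which the test is scheduled.

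| Assessment | Scheduled post-baseline weeks | EOT days landing on an unscheduled week | Count |
|---|---|---|---|
| ECG (both parts) | 8 | 2 to 52 | 52 − 2 + 1 = 51 of 57 |
| Spot urine (Part 1) | 8 | 2 to 52 | 51 of 57 |
| Standing BP | 1 and 8 | 11 to 52 | 52 − 11 + 1 = 42 of 57 |

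An EOT visit on Days 53 to 58 stays at Week 8 for all three. These are counts of days, not probabilities.

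**3. What each table then does.**
- *ECG.* SAP 6.7.4 has two summaries, one by scheduled visit and one shift table at Week 8. A re-numbered ECG belongs to neither. The section defines no last-value or worst-value ECG display, so the record appears only in the listing.
- *Spot urine.* SAP 6.7.2 handles it like the laboratory results, which are shown for each post-baseline visit. The value leaves the Week 8 row but may appear in another week's row.
- *Standing BP.* The by-visit summary uses scheduled visits, so an EOT value on Days 11 to 52 leaves it. The count of subjects with a sitting-to-standing drop has no stated visit limit, so that value may still be counted.

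**4. Size.** The documents give no rate of EOT visits before Day 53. Assume 5% to 10% of about 30 subjects per arm:
- 0.05 × 30 = 1.5 subjects
- 0.10 × 30 = 3 subjects

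SAP 6.2.1.1 takes percentages from the number of subjects in the analysis set unless stated otherwise. One abnormal ECG lost from the shift table therefore changes that arm's percentage by 1/30 = 3.3 points, because the subject stays in the denominator.

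**The case against.** The strongest reply is the sentence in SAP 5.5 that by-visit summaries follow the nominal, or assigned, visit. The eCRF label for this visit is Week 8/EOT. If nominal means that label, early EOT ECGs stay in the Week 8 tables and nothing is lost. One could suppose that re-numbering is meant for the repeated-measures models and the eCRF label for the descriptive tables. The SAP does not say so, and assigned can equally mean the re-numbered visit. If the label governs every by-visit table, it conflicts with a re-numbering rule stated without exception. What stands is that the loss is the literal result of one sentence and uncertain under another.

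Second, stopping drug is not the same as missing Week 8. Protocol 7.1 expects subjects who stop permanently to continue assessments through Week 8, and SAP 5.4 follows them to End of Study. This stands and narrows the point to subjects whose EOT assessments are actually done before Day 53. Examples are unblinded subjects, whom Protocol 6.3 sends to Week 8 assessments when drug is stopped, and subjects who leave the study.

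Third, a reader might infer more than the documents support:
- *That potassium at the time of stopping is lost.* The tie rule can displace an EOT value from a by-visit row when a nominal visit falls in the same window. But SAP 5.5 adds unscheduled values to minimum, maximum and worst-value displays and does not exclude EOT values from them. The potassium shift table in SAP 6.7.2.1 names no visit. Hyperkalemia with dose modification is also tabulated as an event of special interest.
- *That orthostatic falls are understated.* The count has no visit limit, EOT Days 2 to 10 map to Week 1 where standing BP is scheduled, and symptomatic hypotension is both followed weekly and reported as an event of special interest.
- *That the ABPM rule, which takes the last value as EOT, contradicts SAP 5.5.* SAP 7 gives a separate reason: the collection week changed with Amendment 4.

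Finally, all ECG and standing BP values remain in listings, and safety tables carry no formal testing. That limits the consequence but does not put an early leaver's ECG in a table.

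**Conclusion.** The point holds, with ECG as the firm case. Followed literally, SAP 5.5 removes any EOT ECG taken on Days 2 to 52 from both ECG summaries in SAP 6.7.4. The effect is weaker for Part 1 spot urine, which changes row, and for standing BP on Days 11 to 52, which leaves the by-visit summary but not necessarily the orthostatic count.

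The size rests on an assumed early-EOT rate: 1.5 to 3 subjects per arm at 5% to 10% of about 30, and 3.3 percentage points for each abnormal ECG lost. The ambiguous nominal-visit sentence means that two programmers could build different Week 8 ECG tables from the same plan, which is itself reason to correct the text. The documents do not support a broader claim that safety signals are understated across ECG, standing BP, urine and laboratory data. The primary analysis is not affected.

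**What to change.** In SAP 5.5:

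1. Limit day-based re-numbering of the early EOT visit to measures collected weekly: office BP, vital signs and the weekly laboratory tests.
2. For assessments not scheduled weekly (ECG, standing BP, Part 1 spot urine), keep the early record in a Week 8/EOT (last on-treatment) analysis visit whatever the study day. Use that visit in the SAP 6.7.4 shift table and in the by-visit summaries. State which record is used if a subject has both an early EOT assessment and an attended Week 8 visit.
3. Define the nominal (assigned) visit so that it agrees with items 1 and 2.
4. Footnote the Week 8/EOT rows to say that they mix durations of exposure.

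A last on-treatment row for potassium and other key laboratory tests is optional, because nothing in the documents shows that EOT values are excluded from the shift or worst-value displays.

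The cost is a few SAP sentences and minor programming. The Week 8/EOT rows would no longer describe a single exposure time, which the footnote discloses. The primary MMRM is unchanged.

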5.6 Visit Attendance and COVID-19 Impact Assessment

Due to the outbreak of COVID-19 pandemic, visit attendance and how the participation was impacted by COVID-19 will be summarized by treatment group and all subjects pooled together. The summary will contain the number of subjects who attended or missed each scheduled visit and if the visit was affected by the COVID-19 including the specific cause.

Early study discontinuation due to Covid-19 will be summarized in the disposition table as specified in section 6.3.1.

6 STATISTICAL METHODS

6.1 Sample Size Justification

6.2 General Statistical Methods

6.2.1 General Methods

Data are recorded on electronic case report forms (eCRFs). Central laboratory data, PK, at home BP data, and protocol deviation results will be provided via electronic data transfers.

As the primary intent of this study is to provide a preliminary assessment of the relative efficacy of the doses studied, the use of descriptive summary statistics and graphical methods rather than formal statistical tests of significance will be emphasized. Confidence intervals (90% 2-sided) will be used to guide these assessments.

6.2.1.1 Data Display Characteristics

Data displays produced for this study will include three types—summary tables, data listings, and figures. Unless stated otherwise, data listings will be produced for all recorded data. Summary tables will be produced as specified in the following sections. Additional data listings will be produced for outcome measures that involve extensive procedures to derive the analyzed outcomes. Figures will be produced when specified in sections to follow.

Data listings will simply list the data recorded on the CRF or derived for each subject. They will be ordered by treatment, site, subject number, and time of assessment. When expedient, additional levels of ordering hierarchy may reflect subsets of assessments within subject.

Summary tables will display summary statistics calculated for each of the treatment groups, unless described otherwise in following sections. Unless specified otherwise, different columns of a summary table will display the statistics for the different treatment groups. The placebo group statistics will be displayed to the left of the MLS-101 group statistics.

Unless stated otherwise in relevant sections to follow, continuous data will be summarized with the number of nonmissing values, mean, standard deviation, minimum, median, and maximum.

Categorical data will be summarized with the number of nonmissing values and the numbers of values equal to each of the possible values. Percentages of subjects with each of the possible values will be calculated from the number of subjects in the corresponding analysis set, unless stated otherwise. Some continuous variables may also be grouped into categorical levels and evaluated in frequency tables.

6.2.2 Definition of Baseline

Baseline is defined as the last available observed value of the parameter of interest prior to the first administration of the investigational medicinal product (IMP) for the double-blinded treatment period.

For AOBP measurements and any other clinical or laboratory variable for which there are replicate evaluations at the screening and baseline visits, baseline is defined as the mean of the last two non-missing values prior to first administration of the IMP for the double-blinded treatment period.

Change from baseline is calculated as: post-baseline result – baseline result.

Percentage change from baseline is calculated as: (change from baseline / baseline result) x 100%.

